6.4 Description of follow-up visits for mRCC patients in CR (Cases)

Study population: Population of followed-up patients - Cases

Patient follow-up data will be described for the cases at 12 and 24 months:

- Disease progression (Complete response / Partial response / Progression / Stabilisation / Not assessed);
- Sunitinib treatment ongoing (Yes/No);
If yes:
 - Current dose (mg/d);
 - Current regimen (4/2 / 2/1 / Continuous / Other);
A list of the other regimens will be presented.
- Temporary discontinuation of Sunitinib (Yes/No);
If yes:
 - Number of temporary discontinuations per patient
 - The temporary discontinuations will then be described (the statistical unit considered will then be the temporary discontinuation and not the patient):
 - Reason for temporary discontinuation (Progression / Intolerance / Complete response / Local treatment / Other);
A list of the other reasons will be presented.
 - Treatment resumed (Yes/No);
 - Duration of temporary discontinuation (days);
- Permanent discontinuation (Yes/No);
If yes:
 - Reason for permanent discontinuation (Progression / Intolerance / Decision of patient or doctor / Other);
A list of the other reasons will be presented.
 - Duration of treatment with Sunitinib since CR (months);

Patient follow-up data will be described for the cases at the time of the progression:

- Time between CR and progression (months);
 - Duration of additional Sunitinib treatment (pseudo-adjuvant), starting at CR (months)
 - Type of progression (Local Progression/Distant Progression);
If distant progression:
 - at which level (at a known metastatic site/new metastatic site);
 - Location of metastases:
 - Lung (Yes/ No);
 - Bones (Yes/No);
 - Liver (Yes/ No);
 - Adrenal glands (Yes/No);
 - Pancreas (Yes/No);
 - Brain (Yes/No);
-

- Lymph nodes (Yes/No);
If Lymph nodes:
 - Supra-diaphragmatic (Yes/No);
 - Sub-diaphragmatic (Yes/No);
- Recurrence at nephrectomy site (Yes/No) ;
- Other (Yes/ No);
A list of the other locations will be presented.
- Number of metastatic sites;
- Systemic treatment after progression (Yes/No)
- Description of systemic treatments after progression by type of treatment (Bevacizumab with interferon / Bevacizumab without interferon / Sunitinib restart / Sorafenib / Temsirolimus/ Everolimus / Other)
A list of the other systemic treatments will be presented.
A list of systemic treatments including daily dose will be presented.

Patient follow-up data will be described for the cases at the end-of-study visit:

- Best objective response observed after progression (Complete / Partial / Progressive / Stabilised);
- Duration of treatment received after progression with first-line Sunitinib (months);
- Early termination of the study (Yes/No);
- Response achieved (persistent CR since inclusion visit / CR after treatment of recurrence / Disease progression);
- Number of subsequent treatment lines from progression, post CR;
- Death (Yes/ No).

Progression-free survival at the end of the study will be analysed using the Kaplan Meier method, with a presentation of the survival curve. The progression-free survival rate will be estimated with a 95% confidence interval.

6.5 Description of follow-up visits for mRCC patients treated with first-line Sunitinib, non CR (Controls)

Study population: Population of followed-up patients - Controls

Patient follow-up data will be described for the controls at 6 and 12 months of treatment:

- Sunitinib dose (50 mg / 37.5 mg / 25 mg);
- Current regimen (4/2 / 2/1 / Continuous);
- Clinical assessment (Complete Response / Partial Response / Stable Disease / Progression);
If Partial Response:
 - Percentage of tumour reduction (%)
- Location of metastases:
 - Lung (Yes/ No);
 - Bones (Yes/No);
 - Liver (Yes/ No);
 - Adrenal glands (Yes/No);
 - Pancreas (Yes/No);
 - Brain (Yes/No);
 - Lymph nodes (Yes / No); If Lymph nodes:
 - Supra-diaphragmatic (Yes/No);

- Sub-diaphragmatic (Yes/No);
- Recurrence at nephrectomy site (Yes/No) ;
- Other (Yes/ No);
A list of the other locations will be presented.
- Number of metastatic sites;

Patient follow-up data will be described for the controls at the time of the progression:

- Time between initiation of treatment and progression (in months);
- Type of progression (Local Progression/Distant Progression);
If distant progression, at which level (at a known metastatic site/new metastatic site);
- Location of metastases:
 - Lung (Yes/ No);
 - Bones (Yes/No);
 - Liver (Yes/ No);
 - Adrenal glands (Yes/No);
 - Pancreas (Yes/No);
 - Brain (Yes/No);
 - Lymph nodes (Yes / No); If Lymph nodes:
 - Supra-diaphragmatic (Yes/No);
 - Sub-diaphragmatic (Yes/No);
 - Recurrence at nephrectomy site (Yes/No) ;
 - Other (Yes/ No);
A list of the other locations will be presented.
- Number of metastatic sites;

Patient follow-up data will be described for the controls at the end-of-study visit:

- Patients still receiving Sunitinib (Yes/No);
If yes:
 - Response (Complete Response / Partial Response / Stable Disease / Progression);
- If No:
 - Progression (Yes/ No);
 - Duration of Sunitinib treatment (months);
 - New treatments (Yes/No);
A list of new treatments will be presented.
- Number of subsequent treatment lines.
- Early termination of the study (Yes/No);
- Death (Yes/ No).

Progression-free survival at the end of the study will be analysed using the Kaplan Meier method, with a presentation of the survival curve. The progression-free survival rate will be estimated with a 95% confidence interval.

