- Visit (Yes/ No);
- Date of visit;
- Best response to treatment received post-progression;
- Duration of administration after progression with first-line Sunitinib;
- Last news: premature discontinuation of study, date of last news, persistent CR since inclusion visit, CR after treatment of post-CR progression, disease progression, number of subsequent lines after progression, post CR;
- Death (Yes/No), date of death.

For Controls

At the 6-month and 12-month follow-up visits of Sunitinib treatment:

- Date of visit;
- Clinical assessment using RECIST criteria (response to treatment, if progression: date of progression, progression at a known metastatic site or at a new site);
- Metastatic sites: location and number of metastatic sites;
- Blood sample and collection date.

If progression:

- Date of visit;
- Date of progression, type of progression (local or distant);
- Metastatic sites: location and number of metastatic sites;
- Blood sample and collection date

At the end-of-research visit (36 months after the inclusion visit):

- Visit (Yes/ No);
- Date of visit;
- Patient still treated with Sunitinib, if yes: response to treatment, if no: progression, new treatment, date of Sunitinib discontinuation;
- Number of subsequent treatment lines;
- Last news: study stopped prematurely, date of last news;
- Death (Yes/No), date of death.

Centralised review of Computerised Tomography Scan (CT Scan) - only for patients in CR

In this research, two of the scans of CR patients (Cases) will be reviewed centrally.

- The scan at initiation of first-line Sunitinib;
- The scan showing CR.

This review will take place between the screening visit and the inclusion visit of the patient. Thus a patient can only be included after the scans have been reviewed to validate the CR.

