If the day is missing, it will be replaced by the first day of the month.
If the month is missing, only the year will be used.*
- Time between CR and progression (in months):
(Date of progression - Date of CR) / 365.25 x 12
*Note: In case of incomplete dates (date of CR or date of progression):
If the day is missing, it will be replaced by the first day of the month.*
- Progression-free survival (in months):
It is defined as the time between CR and progression or death.
(Date of the event - Date of CR) / 365.25 x 12
Note: Patients who have not progressed and who have not died will be censored at the date of last visit.

Event	Censor decision	Date of the event or censor
Progression	Non-censored	Date of progression
All-cause death without progression	Non-censored	Date of death
Lost to follow-up	Censored	Date of last visit
End of study without progression or death	Censored	Date of last news

For Controls:

- Time between initiation of treatment and progression (in months):
(Date of progression - Date of treatment initiation) / 365.25 x 12
*Note: In case of incomplete dates (date of treatment initiation or date of progression):
If the day is missing, it will be replaced by the first day of the month.*
- Progression-free survival (in months):
It is defined as the time between treatment initiation and progression or death.
(Date of the event - Date of treatment initiation) / 365.25 x 12
Note: Patients who have not progressed and who have not died will be censored at the date of last visit.

Event	Censor decision	Date of the event or censor
Progression	Non-censored	Date of progression
All-cause death without progression	Non-censored	Date of death
Lost to follow-up	Censored	Date of last visit
End of study without progression or death	Censored	Date of last news

- Duration of treatment with Sunitinib (in months):
(Date of treatment discontinuation - Date of treatment initiation + 1) / 365.25 x 12
*Note: In case of incomplete dates (initiation date or discontinuation date):
If the day is missing, it will be replaced by the first day of the month.*

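### Sunitinib duration is described only after stopping (or, for one Case item, at progression), so read as time on treatment it tends to be too short

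*SAP*

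**What the plan says.** **Controls.** At the end-of-study visit, SAP 6.5 first asks "Patients still receiving Sunitinib (Yes/No"). The yes branch lists only response. The no branch lists progression, new treatments and "Duration of Sunitinib treatment (months"). SAP 5.2, under its Controls list, derives the duration in months from "Date of treatment discontinuation - Date of treatment initiation + 1", so a stop date is needed. SAP 2.3 collects that date only on the no branch: "Patient still treated with Sunitinib, if yes: response to treatment, if no: progression, new treatment, date of Sunitinib discontinuation".

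**Cases.** At 12 and 24 months, SAP 6.4 asks "Permanent discontinuation (Yes/No") and, if yes, describes "Duration of treatment with Sunitinib since CR (months"). SAP 5.2 gives no derivation for this variable. A second item, "Duration of additional Sunitinib treatment (pseudo-adjuvant), starting at CR (months"), is described at the time of progression.

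**Missing data and censoring.** SAP 5.1 rules out replacing missing values except where the SAP says otherwise, and no exception covers a patient with no stop date because treatment continues. The only censoring tables (SAP 5.2) and Kaplan-Meier analyses (SAP 6.4 and 6.5) are for progression-free survival.

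**The concern.** Time on treatment is a time-to-event variable that is right-censored in anyone still treated at the last contact. A mean or median taken only over those who stopped conditions on the event having happened within follow-up. It therefore favours short durations.

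What is at stake is descriptive. Describing whether CR patients continue or discontinue systemic treatment is the first secondary objective (SAP 2.2.2). A reader of the final report is likely to take a duration since CR as how long such patients stay on Sunitinib, although those who continue are the ones left out. For Controls the duration serves no stated objective, but it would be reported and could be quoted as treatment exposure.

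**Working it through.** **Which patients get a duration**

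| Item | Described in | Left out |
|---|---|---|
| Controls, Sunitinib duration (SAP 6.5) | Stopped by end-of-study visit | Still on Sunitinib |
| Cases, duration since CR (SAP 6.4, 12 and 24 months) | Permanent discontinuation | Still on Sunitinib, or only interrupted |
| Cases, pseudo-adjuvant duration (SAP 6.4) | Progression | No progression, including event-free continuers |

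**Direction.** Let F be the distribution of time to stopping and c a fixed cut-off. Among stoppers, the probability of having stopped by t is F(t)/F(c), which is at least F(t). The stoppers-only distribution is therefore shifted towards short times for any F with some patients still treated at c.

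**Size in Controls.** The plan gives no figure for time on treatment to reproduce. Its only design figure, 80% power for d = 0.55 with 40 and 80 patients, reproduces at 80.4% with the t distribution, and this point does not depend on it. Inputs:

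- n = 80 Controls (SAP 2.5) and follow-up τ = 36 months (SAP 2.3).
- Assumed: exponential stopping with true median m of 6, 11 or 15 months. The ends of this range are borrowed from the 6 to 15 months to resistance in SAP 2.1, which is not a time-on-treatment figure; 11 is a value in between.

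Formulas, with λ = ln 2 / m and F = 1 − 2^(−τ/m):

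- Expected number still treated = 80(1 − F)
- Stoppers-only median = −ln(1 − F/2)/λ
- Stoppers-only mean = 1/λ − τ(1 − F)/F
- Mean time on treatment up to τ, all patients = F/λ

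For m = 15: λ = 0.0462 and F = 1 − 2^(−2.4) = 0.811. The median is −ln(0.595)/0.0462 = 11.2 months, and 1 − 11.2/15 = 25%.

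| True median (months) | Still treated of 80 | Stoppers-only median | Too low by | Stoppers-only mean | Mean to 36 months, all patients |
|---|---|---|---|---|---|
| 6 | about 1 | 5.9 | 2% | 8.1 | 8.5 |
| 11 | about 8 | 9.4 | 14% | 11.7 | 14.2 |
| 15 | about 15 | 11.2 | 25% | 13.2 | 17.5 |

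**Cases, illustration only.** The same model at 36 months with true medians of 24 and 36 months gives stoppers-only medians of 13.5 and 14.9 (44% and 58% low). With a 24-month cut-off, the last annual visit described, true medians of 15 and 24 months give 8.8 and 10.0 (41% and 58% low). These show how the bias grows as more patients continue; they do not predict it.

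**Does Kaplan-Meier cure it?** In 1,000 simulated trials per setting with a 36-month cut-off and continuing patients censored, true medians of 11 and 15 months (n = 80) were estimated at 11.2 and 15.2, and 24 months (n = 40) at 24.4. With a true median of 36 months, the median is often not reached within follow-up.

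**The case against.** The strongest defence is that the conditioning is in plain sight. The Control item sits directly under the question whether the patient is still on Sunitinib, so the number ongoing is reported beside it, and the SAP never calls the result time on treatment for everyone. The secondary objective is also served without conditioning on stopping: SAP 6.3.2 describes strategy after CR for all included Cases, and SAP 6.4 describes ongoing treatment, interruptions and permanent discontinuation at 12 and 24 months. This stands. The SAP makes no false statement; it lacks an estimate of how long patients stay on treatment.

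Stronger readings are tempting and are not supported:

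- *Every Sunitinib duration is limited to patients who stopped.* The pseudo-adjuvant item depends on progression instead. It still omits event-free continuers, so it does not fill the gap.
- *Case durations will be understated by about half.* The documents give no distribution. CR may precede inclusion by up to 5 years (Protocol 8.2.3), so follow-up from CR differs by patient, and some Cases may stop at CR itself. A fixed 36-month clock does not fit.
- *Continuing patients always have the longest durations, so the error has a certain sign.* A Case with recent CR may be continuing after a short time. The SAP 5.2 formula does not subtract interruptions. The Control form (Protocol Appendix 6) asks for the stop date in its 36-month section, so early deaths and withdrawals with short exposure may have none. The last two push the summary upward.
- *The case-control comparison is affected.* Duration is not among the variables compared in SAP 6.3.
- *All dates are already collected.* The Case inclusion form (Protocol Appendix 5) records discontinuation as yes or no without a date.

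**Conclusion.** The point holds as a limited improvement to a descriptive analysis. In both groups, patients who continue Sunitinib without an event contribute no duration, and no censored analysis makes up for this. Read as time on treatment, the summaries tend to be too short whenever some patients are still treated at cut-off.

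For Controls the shortfall in the median is about 2% to 25%, under exponential stopping, a common 36-month cut-off and true medians of 6 to 15 months. It is negligible if nearly all stop within follow-up. For Cases it could be larger if many continue, but no figure from the documents fixes its size. The primary comparison and the sample size are unaffected.

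**What to change.** In SAP 5.2, 6.4 and 6.5:

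- Define time to permanent Sunitinib discontinuation for all followed-up patients, from Sunitinib start in Controls and from CR in Cases, and add the missing Case derivation.
- Censor patients still treated at the last visit with known Sunitinib status. For Cases this may be an annual visit, because their end-of-study form does not ask for it.
- Report Kaplan-Meier estimates with 95% confidence intervals and the number ongoing. Keep the stoppers-only summary, labelled as conditional on having stopped.
- For Cases, allow for late entry at inclusion, or start the clock at inclusion among those still treated. Either way, count those who had already stopped by inclusion separately.
- State how death on treatment, temporary interruptions and missing stop dates are handled.

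The cost is a SAP edit and one more run per group of a method already planned. The downsides are a few extra derivation rules, some stop dates that may be missing, and a median that may not be reached. If it is not reached, report that, with the proportion still treated at fixed times.

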6.6 Description of adverse events

Study population: Population of followed-up patients

The number of AEs, the number and percentage of patients with at least one AE will be described by group for the following event categories:

- All AEs by system organ class,
- All AEs likely to be related to the study drug ('Yes' or Missing response method) by system organ class,
- All serious AEs by system organ class,
- All serious AEs likely to be related to the study drug ('Yes' or Missing response method) by organ class,

The AEs will be described according to severity, action taken regarding the study treatment, and progression.

AEs reported during the study will be coded using the MedDRA dictionary, version 20.0.

ANNEX 1. ANALYSIS TABLES - MODELS

Study: A6181209 - OVERVIEW
Group: XXXXX

Page X / N

Table X - Patient layout

	Cases	Controls	Total
Active doctors			xx
All patients	xx	xx	xx
Patients included	xx	xx	xx
Patients followed-up	xx	xx	xx

Name of the SAS programme: P:\XXXXX\XXXX\Analyse\Pgm\nom_du_programme.sas

Date and time when programme was executed: DDMMYYYY HH:MM

Study: A6181209 - OVERVIEW
Group: XXXXX

Page X / N

Table X - Layout of visits

	Cases (N=XX)	Controls (N=XX)
Number of patients at each visit		
Screening visit	xx (xx.x%)	
Inclusion visit	xx (xx.x%)	xx (xx.x%)
Visit at 6 months		xx (xx.x%)
Visit at 12 months	xx (xx.x%)	xx (xx.x%)
Visit at 24 months	xx (xx.x%)	
Visit with diagnosis of progression	xx (xx.x%)	xx (xx.x%)
End-of-study visit	xx (xx.x%)	xx (xx.x%)
Time between inclusion and 12-month visit		
n	x	x
Mean (standard deviation)	xx.x (xx.x)	xx.x (xx.x)
Median	xx.x	xx.x
Min. ; Max.	xx; xx	xx; xx
Missing data	x	x
...		
Total length of follow-up (months)		
n	x	x
Mean (standard deviation)	xx.x (xx.x)	xx.x (xx.x)
Median	xx.x	xx.x
Min. ; Max.	xx; xx	xx; xx
Missing data	x	x

Name of the SAS programme: P:\XXXXX\XXXXX\Analyse\Pgm\nom_du_programme.sas

Date and time when programme was executed: DDMMMYYYY HH:MM

Study: A6181209 - OVERVIEW
Group: XXXXX

Table X - Description / Analysis of qualitative and quantitative variables

	Cases (N=XX)	Controls (N=XX)	p
Quantitative variable			x.xxx (T)
n	xx	xx	
Mean (standard deviation)	xx.x (xx.x)	xx.x (xx.x)	
Median	xx.x	xx.x	
Min. ; Max.	xx; xx	xx; xx	
Missing data	xx	xx	
Qualitative variable			x.xxx (C)
n	xx	xx	
Category 1	xx (xx.x%)	xx (xx.x%)	
...	
Modality n	xx (xx.x%)	xx (xx.x%)	
Missing data	xx	xx	
(T) Student's t test / (W) Wilcoxon test (C) Chi-2 test / (F) Fisher test ...			

Name of the SAS programme: P:\XXXXX\XXXX\Analyse\Pgm\nom_du_programme.sas
Date and time when programme was executed: DDMMMYYYY HH:MM

Study: A6181209 - OVERVIEW
Group: XXXXX

Page X / N

Table X - Qualitative and Quantitative Variables - Case Versus Control Comparison

	Total (N=XX)
Normal quantitative variable - Difference in means [95% CI]	xx.x [xx.x ;xx.x]
Non-normal Quantitative variable - Hodges Lehmann estimator [95% CI]	xx.x [xx.x ;xx.x]
Qualitative variable - Odds Ratio [95% CI]	xx.x [xx.x ;xx.x]

Name of the SAS programme: P:\XXXXX\XXXX\Analyse\Pgm\nom_du_programme.sas

Date and time when programme was executed: DDMMMYYYY HH:MM

Study: A6181209 - OVERVIEW
Group: XXXXX

Page X / N

Table X - Progression-free survival analysis (months) - Kaplan-Meier

	Total (N=XX)
Progression-free survival (months)	
Number of subjects	99
Event	99 (99.9)
Censored*	99 (99.9)
Min	99.9
Max	99.9
Q3 [95% CI]	99.9 [99.9;99.9]
Median [95% CI]	99.9 [99.9;99.9]
Q1 [95% CI]	99.9 [99.9;99.9]
Mean progression-free survival [95% CI]	99.9 [99.9;99.9]

Name of the SAS programme: P:\XXXXX\XXXXX\Analyse\Pgm\nom_du_programme.sas

Date and time when programme was executed: DDMMYYYY HH:MM

Study: A6181209 - OVERVIEW
Group: XXXXX

Table X – Description of adverse events (AE) by System Organ Class (SOC) and Preferred term (PT)

	Cases (N=XX)		Controls (N=XX)	
	Nb of events	Nb (%) of patients	Nb of events	Nb (%) of patients
At least one adverse event	xx	x (xx.x%)	xx	x (xx.x%)
Body system 1	xx	xx (xx.x%)	xx	xx (xx.x%)
Preferred term 1	xx	xx (xx.x%)	xx	xx (xx.x%)
Preferred term 2	xx	xx (xx.x%)	xx	xx (xx.x%)
...				
Preferred term n	xx	xx (xx.x%)	xx	xx (xx.x%)
Body system 2	xx	xx (xx.x%)	xx	xx (xx.x%)
Preferred term 1	xx	xx (xx.x%)	xx	xx (xx.x%)
Preferred term 2	xx	xx (xx.x%)	xx	xx (xx.x%)
...				
Preferred term n	xx	xx (xx.x%)	xx	xx (xx.x%)
....				
Body system n	xx	xx (xx.x%)	xx	xx (xx.x%)
Preferred term 1	xx	xx (xx.x%)	xx	xx (xx.x%)
Preferred term 2	xx	xx (xx.x%)	xx	xx (xx.x%)
...				
Preferred term n	xx	xx (xx.x%)	xx	xx (xx.x%)

Name of the SAS programme: P:\XXXXX\XXXX\Analyse\Pgm\nom_du_programme.sas

Date and time when programme was executed: DDMMMYYYY HH:MM

Study: A6181209 - OVERVIEW
Group: XXXXX

Table X - Description of adverse events

	Cases (N=XX)	Controls (N=XX)
Qualitative variable		
n	xx	xx
Category 1	xx (xx.x%)	xx (xx.x%)
...
Modality n	xx (xx.x%)	xx (xx.x%)
Missing data	xx	xx
Note: the unit of analysis is the adverse event		

Name of the SAS programme: P:\XXXXX\XXXX\Analyse\Pgm\nom_du_programme.sas
Date and time when programme was executed: DDMMYY HH:MM

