(dd/mm/yyyy)

Progression at a known metastatic site

Yes No

New metastatic site

Yes No

METASTATIC SITES

LOCALIZATION OF METASTASES

YES **NO**

- Lungs
- Bone
- Liver
- Adrenal glands
- Pancreas
- Brain
- Lymph nodes
 - o Supradiaphragmatic
 - o Infradiaphragmatic
- Recurrence at the nephrectomy renal bed
- Other

(please specify):

NUMBER OF METASTATIC SITES: |____|

BLOOD SAMPLING DURING PROGRESSION

YES **NO**

- Blood sample of 2 times 5 ml

Sampling date |_____|_____|_____|_____|_____|_2_|_0_|_1_|____| (dd/mm/yyyy)

**Data relating to the end of study visit of patients NOT in CR
(36 months)**

Did the patient attend a visit at 36 months	YES 	NO 
Visit date __ __ __ __ _2_ _0_ _1_ __ (dd/mm/yyyy)		
Is the patient still being treated with Sunitinib? YES		NO 
If yes, is the patient presenting a:		
PARTIAL RESPONSE	YES 	NO 
COMPLETE RESPONSE	YES 	NO 
STABLE DISEASE	YES 	NO 
PROGRESSION	YES 	NO 
If no, is the patient presenting disease PROGRESSION	YES 	NO 
Please specify the new treatment:		
Sunitinib discontinuation date __ __ __ __ _2_ _0_ _1_ __		
Number of previous lines of treatment.....		
LATEST INFORMATION		
Did the patient withdraw from study prematurely? YES	 NO 	
Latest information date: __ __ __ __ _2_ _0_ _1_ __ (dd/mm/yyyy)		

DEATH		
YES 	NO 	
Date of death: __ __ __ __ _2_ _0_ _1_ __ (dd/mm/yyyy)		

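### AE severity and action taken on Sunitinib are described per event, so the plan gives no count of patients with a severe AE in either group and no count of Controls who stopped for toxicity

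*SAP*

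**What the plan says.** AEs are one of the three endpoints in SAP 2.4. SAP 6.6 sets the analysis set ("Study population: Population of followed-up patients") and plans two kinds of summary.

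- **Per patient.** For four categories (all AEs, AEs likely related to the drug, serious AEs, serious AEs likely related), "the number and percentage of patients with at least one AE will be described by group", by system organ class. The matching Annex 1 model starts with the row "At least one adverse event" and has event and patient columns. It has no split by severity or action taken.
- **Attributes of the AEs.** "The AEs will be described according to severity, action taken regarding the study treatment, and progression". The sentence mentions no patient count. The remaining Annex 1 AE model, for an unnamed qualitative variable with counts and percentages by group, carries the footnote "Note: the unit of analysis is the adverse event".

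Stopping Sunitinib is handled differently in the two groups.

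- **Cases (SAP 6.4, at 12 and 24 months).** Permanent discontinuation is described with "Reason for permanent discontinuation (Progression / Intolerance / Decision of patient or doctor / Other" as the list of reasons.
- **Controls (SAP 6.5, end-of-study visit).** For patients no longer on Sunitinib, the plan lists "Progression (Yes/ No", then treatment duration and new treatments. The Control CRF (Protocol Appendix 6, 36-month visit) asks "If no, is the patient presenting disease PROGRESSION", and records the new treatment and the stop date. Neither asks why Sunitinib was stopped.

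**The concern.** A reader of a safety section wants to know how many patients had a severe AE and how many stopped the drug because of one. A percentage of events answers neither question. Its denominator grows with every mild event recorded, and several events in one patient count separately. The serious-AE table does not fill the gap: Protocol section 10 defines seriousness by consequences such as death, hospitalization or disability, or by medical importance, so a severe AE without such a consequence can be absent from it.

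For Controls, the end-of-study progression item is not a reason for stopping. A Control off drug without progression may have stopped for toxicity, by choice or for another reason. A Control who stopped for toxicity and progressed later can be recorded as progression. The per-AE action-taken field is therefore the one planned source for toxicity stops in Controls, and it is summarized by event.

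**Working it through.** **What can be reproduced.** The plan gives no AE rate, so it has no figure of its own on this point. Only the group sizes come from the documents: 40 Cases and 80 Controls (SAP 2.5). The followed-up population may be smaller. Every AE rate below is an assumption.

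**Step 1: which patient-level numbers are planned.**

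| Quantity | Cases | Controls |
|---|---|---|
| Any, related, serious, serious related AE | yes (SAP 6.6) | yes (SAP 6.6) |
| Death | yes (SAP 6.4) | yes (SAP 6.5) |
| Severe AE, or worst severity | no | no |
| Permanent stop for toxicity | yes, at 12 and 24 months (SAP 6.4) | no |

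**Step 2: what an event percentage measures.** Let q be the share of patients with a severe AE, s the number of severe AEs per affected patient, and m the number of AEs of any severity per patient. Then

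share of events = (q × s) / m.

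The patient share q cannot be recovered from this without s and m for severe events, and the event count does not settle it either. Take 24 severe events among 480 in 80 Controls, which is 24/480 = 5.0% of events:

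- one each in 24 patients: 24/80 = 30.0% of patients;
- two each in 12 patients: 12/80 = 15.0%;
- four each in 6 patients: 6/80 = 7.5%.

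The event table is identical in all three.

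**Step 3: dilution.** Suppose 16 of 80 Controls (20%) each have one AE leading to a permanent stop. The event percentage is 16/(80 × 5) = 4.0% at 5 AEs per patient, 16/(80 × 10) = 2.0% at 10, and 16/(80 × 20) = 1.0% at 20.

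**Step 4: can the order of the groups change?** With s = 1 in both groups, the group with the higher patient share shows the lower event share when its ratio of AEs per patient to the other group exceeds the ratio of patient shares. For 30% against 20%, the threshold is 30/20 = 1.5.

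| AEs per patient (Controls, Cases) | Controls: 24 of 80 patients (30.0%) | Cases: 8 of 40 patients (20.0%) | Order of event shares |
|---|---|---|---|
| 4 and 4 | 24/320 = 7.5% | 8/160 = 5.0% | kept |
| 3 and 2 | 24/240 = 10.0% | 8/80 = 10.0% | tied |
| 6 and 2 | 24/480 = 5.0% | 8/80 = 10.0% | reversed |

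**Step 5: is a difference in AEs per patient plausible?** Protocol section 10 starts the reporting period at the first dose, or at consent for patients already exposed. Controls are therefore followed from the start of Sunitinib. Cases enter after a remission that may lie up to 5 years back, and some have discontinued the drug. Unequal AE counts are possible by design, but the documents do not say how unequal.

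**The case against.** - **Event-level description is legitimate.** With the unit stated openly, it is not an error. This stands. The gap is that nothing patient-level accompanies it.
- **A reader might infer that the plan never reports how many patients stopped Sunitinib for toxicity.** The documents do not support that for Cases, since SAP 6.4 tabulates intolerance as a reason for permanent discontinuation. That covers 12 and 24 months of a 36-month follow-up, and reasons for temporary stops use the discontinuation as the unit. The gap is complete only for Controls.
- **A reader might infer that fatal events are lost in the event percentages.** They are not. Death is described per patient in both groups, and under Protocol section 10 a fatal event is a serious AE, so it enters the patient-level serious-AE table.
- **A reader might infer that the tables will rank the groups wrongly.** Step 4 shows only that this can happen. It rests on assumed rates, SAP 6.6 plans no test, and no study objective concerns safety. Patient percentages would not give a valid ranking either, because the exposure windows differ. This objection stands in full.
- **The table model is generic.** It names neither severity nor action taken, so the link to SAP 6.6 is an inference. It is the only AE model that fits. The word progression in the SAP 6.6 list probably means AE outcome, but nothing here depends on that reading.

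**Conclusion.** The point holds as a reporting gap in a descriptive safety section. Two numbers are missing: patients by worst severity in both groups, and Controls who stopped Sunitinib for toxicity. Without the second, stopping for toxicity cannot be set side by side per patient in the two groups.

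The size cannot be stated from the documents. Under the assumptions shown, an event percentage of 5.0% is compatible with 7.5% to 30.0% of Controls affected. A 20% patient share of toxicity stops prints as 1.0% to 4.0% of events. Reversal of the group order is possible but not shown to be likely. The conclusion rests on reading the generic Annex 1 model as the one meant for severity and action taken. The primary comparison of patient characteristics is untouched. Because AEs are a listed endpoint and the remedy is cheap, the change should be made.

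**What to change.** In SAP 6.6 and Annex 1, add the number and percentage of followed-up patients per group, for all AEs and for related AEs:

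- (a) by worst severity, each patient counted once;
- (b) with at least one AE leading to permanent discontinuation of Sunitinib and, where the AE form separates them, to temporary interruption or dose reduction.

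Keep the event-level table as a labelled supplement; dropping its percentages is optional. In SAP 6.5, cross-refer Controls who are off Sunitinib to (b), so that stops for toxicity can be told apart from other stops. Add a sentence that AE percentages cover different exposure windows (Controls from first dose, already-exposed Cases from consent) and are descriptive, not a comparison of risk.

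SAP 6.6 already plans to describe severity and action taken for each AE, so this re-aggregates planned data by patient. The cost is SAP wording, one added table model and a slightly longer AE output. The full AE form is not visible in the public text, so the categories of its action-taken field should be checked before (b) is finalized.
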